8.1.1 Primary Outcome Measures

The primary outcome measure is the proportion of patients who have a non-diagnostic (Thy 1) FNAC result following first FNAC compared between the RTE-FNAC and US-only guided FNAC.

8.1.2 Secondary Outcome Measures

The secondary outcome measures for the study are:

- 1. Number of FNACs needed to obtain a definitive diagnosis in each patient;
- 2. Time from first FNAC to obtaining a definitive diagnosis in each arm;
- 3. The proportion of patients with a benign histology, compared between arms;
- 4. The proportion of patients who have a non-diagnostic (Thy 1) cytology result following any FNAC by arm;
- 5. The proportion of patients who receive surgery by arm;
- 6. Accuracy of 1st FNAC results and repeated FNAC results, compared between arms;
- 7. If RTE or US without FNAC is as accurate as RTE or US with FNAC, compared between arms;
- 8. Patient reported anxiety, pain and quality of life(by the HADS questionnaire, VAPS and EQ-5D) at baseline and at 3, 6 and 12 months post-randomisation;
- 9. Radiologist survey-completed by radiologists at the end of the procedure to identify whether radiologists found RTE had contributed to their decisions, ease of use, and their prediction of malignancy of the nodule using RTE or US features alone;
- 10. Complication rate from any thyroidectomy at 30-days and 6 months post-surgery haematoma rate and temporary hypocalcaemia at 30 days and vocal cord palsy and permanent hypocalcaemia rate at 6 months.
- 11. Resource usage for consultation time and diagnostic testing procedures and subsequent management including consultations and surgical treatments.

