11.6. Confidentiality of Personal Data	
11.7. Publication	
REFERENCE LIST	27

ELATION TRIAL SUMMARY

Trial design: Pragmatic randomised controlled trial with 1:1 randomisation.

Objectives: The primary objective is to determine if real time elastography (RTE) in conjunction with fine needle aspiration cytology (FNAC) will reduce the number of patients who have a non-diagnostic **first** FNAC result as compared to conventional ultrasound (US) only guided FNAC.

Outcome measures

Primary outcome measure

The proportion of patients who have a non-diagnostic (Thy1) cytology result following the first FNAC.

Secondary Outcome measures

- 1. Number of FNACs required to obtain a definitive diagnosis¹;
- 2. Time from first FNAC to obtaining a definitive diagnosis;
- 3. The proportion of patients with benign histology results following thyroidectomy;
- 4. Proportion of patients who have thyroidectomy;
- 5. Accuracy of a cytology result for first FNAC and repeated FNAC in relation to overall definitive diagnosis;
- 6. Accuracy of an imaging assessment on ultrasound (with or without RTE) alone diagnostic protocol in relation to overall definitive diagnosis;
- 7. Patient reported outcome measures of depression and anxiety, pain, and quality of life: the Hospital Anxiety and Depression rating Scale (HADS), Visual Analogue Pain Score (VAPS) and EQ-5D quality of life score;
- 8. Radiologist report of whether RTE had contributed to the radiologist's decisions, how easy they found using RTE, and whether they found it helpful above using US-alone in predicting malignancy;
- 9. Complication rate from any thyroidectomy at 30-days and 6-months post-surgery to include haematoma rate and temporary hypocalcaemia rate at 30 days and vocal cord palsy and permanent hypocalcaemia at 6 months post-operative;

¹ Definitive diagnosis is defined as: obtaining two benign (Thy 2) FNAC results; obtaining a single benign (Thy 2) result with a U2 benign ultrasound; obtaining histopathological diagnosis following a Thy 3, Thy 4, or Thy5 result; or obtaining histopathological diagnosis following persistently non-diagnostic (Thy 1) FNAC results

10. Resource usage for consultation time and diagnostic testing procedures and subsequent

management including consultations and surgical treatments.

Eligibility criteria

Inclusion criteria

1. Patients with single or multiple thyroid nodules whether solid or partially cystic (ie: mixed),

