7.1. Follow-up assessments

Follow-up will be undertaken for 1 year from randomisation or until definitive diagnosis has been obtained if not achieved during that first year. This will be sufficient time to allow for further FNACs if required after the first test. Also this allows sufficient time for any surgery to be undertaken and histological diagnosis to be available.

For both intervention and control arms, diagnosis and management will proceed as follows:

Thy1 - repeat FNAC, especially if suspicion of malignancy. If Thy1 on three FNACs, then the recommendation is made for diagnostic surgery.

Thy 2 - repeat FNAC within 3-6 months. If two benign (Thy2) FNAC results are obtained then patient can be discharged. Consideration for discharge with a U2 scan and one Thy2 is allowed, but is not recommended for the purposes of this study.

Thy 3a - repeat FNAC within 3-6 months or discussion with MDT. Surgery may then be advised

Thy3/3f/4/5 - surgery is necessary.

All repeat FNAC must be undertaken using the same ultrasound technique as the first one specified by the randomisation and ideally by the same RTE-accredited radiologist.

All follow-up data will be captured on the relevant CRF and returned to the ElaTION Trial Office.

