8. STATISTICAL CONSIDERATIONS

8.1. Outcome Measures

The reference standard for all FNAC assessments and results is the final definitive diagnosis.

Final definitive diagnosis is defined as:

- obtaining two benign (Thy 2) FNAC results;
- or obtaining one Thy2 FNAC with a U2 scan;
- or obtaining histopathological diagnosis following a Thy 3, Thy 3f, Thy 4, or Thy5 result;
- or obtaining histopathological diagnosis following persistently non-diagnostic (Thy 1) FNAC results.

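### Repeat-FNAC accuracy is to be compared between arms, but the first FNAC result decides who has a repeat, so this is not a randomised comparison and can mislead in either direction

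*Protocol*

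**What the plan says.** Protocol 8.1.2, item 6, lists "Accuracy of 1st FNAC results and repeated FNAC results, compared between arms". The Trial Summary (secondary outcome 5) has the same outcome without the between-arm wording: "Accuracy of a cytology result for first FNAC and repeated FNAC in relation to overall definitive diagnosis".

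Protocol 8.4.2 includes, among its comparisons of proportions, how a benign first result compares in accuracy with later FNACs. It assigns the whole list to a between-arm mixed model adjusted for the minimisation variables. McNemar's test is reserved for comparing tests within an arm.

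Protocol 7.1 sets the pathway in both arms:

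- "Thy1 - repeat FNAC, especially if suspicion of malignancy"
- "Thy 2 - repeat FNAC within 3-6 months"
- "Consideration for discharge with a U2 scan and one Thy2 is allowed" (although discouraged for this study)
- "Thy 3a - repeat FNAC within 3-6 months or discussion with MDT"
- "Thy3/3f/4/5 - surgery is necessary"

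Protocol 8.1 adds: "The reference standard for all FNAC assessments and results is the final definitive diagnosis". Two Thy2 results, or one Thy2 with a U2 scan, count there as a definitive benign diagnosis.

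**The concern.** Randomisation makes the arms comparable at the first FNAC. It does not make the patients who reach a second FNAC comparable, because they are selected by the result of the randomised procedure. Protocol 5.1 gives improved accuracy of the first FNA as a purpose of RTE. If RTE achieves this, it changes both how many cancers remain for a repeat and which kind they are. The minimisation variables are baseline characteristics and cannot undo that. Protocol 8.4 says that all patients are analysed as allocated, but a patient sent straight to surgery has no repeat result to analyse.

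At stake is a reported difference in repeat-FNAC accuracy that is partly or wholly selection. It would stand beside the first-FNAC result as though it had the same randomised status.

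**Working it through.** **1. The plan's own figure.** The protocol gives no number for repeat-FNAC accuracy. Its only calculation is for the primary outcome (Protocol 8.2), and it reproduces. For 10% v 4%, two-sided 5%, 90% power:

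- n = [1.96·√(2·0.07·0.93) + 1.2816·√(0.09 + 0.0384)]² / 0.06² = 378 per arm
- with continuity correction, 411 per arm, or 822 in total
- 411/0.85 = 483.5, so 484 per arm, or 968

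This point does not disturb that calculation.

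**2. The repeat groups differ if the trial's hypothesis is true.** Take Thy1 at 10% v 4% (Protocol 8.2). Assume that 10% of each arm go straight to surgery, which is the audit's Thy3 to Thy5 total of 5 + 3 + 2 in Protocol 1.2, and that the rest are Thy2 and all repeated. Thy1 patients are then 10/90 = 11.1% of repeaters with ultrasound (US) and 4/90 = 4.4% with RTE.

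**3. Effect on sensitivity.** The detection rates here are assumptions; the documents give none. Let 60% of cancers be easy to detect and 40% hard. Each arm has the same detection rate at both FNACs, and cancers missed at the first FNAC go on to a repeat.

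- US detects 0.8 of easy and 0.3 of hard cancers.
- First FNAC: 0.6·0.8 + 0.4·0.3 = 0.60.
- Left for repeat: easy 0.12, hard 0.28, total 0.40.
- Repeat: (0.12·0.8 + 0.28·0.3)/0.40 = 0.18/0.40 = 45%.

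The true difference below is the one that would be seen if every cancer had the repeat. It equals the first-FNAC difference.

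| RTE detection, easy/hard | First, RTE (US 60%) | Left for repeat | Repeat, RTE (US 45%) | True difference | Repeat difference |
|---|---|---|---|---|---|
| 1.0/0.3 | 72% | 0.28 | 0.084/0.28 = 30% | +12 | −15 |
| 0.9/0.3 | 66% | 0.34 | 0.138/0.34 = 40.6% | +6 | −4.4 |
| 0.9/0.4 | 70% | 0.30 | 0.150/0.30 = 50% | +10 | +5 |
| 0.8/0.5 | 68% | 0.32 | 0.196/0.32 = 61.3% | +8 | +16.3 |

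If all cancers are equally detectable (US 80%, RTE 90%), the repeat shows 80% v 90% and there is no distortion. Selection can therefore reverse, shrink, leave alone or exaggerate the true difference.

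**4. Numbers.** Malignancy of 4–7% (Protocol 1.1) in 484 patients gives 19 to 34 cancers per arm. At an assumed 5% there are 24.2. Those reaching a repeat number 24.2·0.40 = 9.7 with US and 24.2·0.28 = 6.8 to 24.2·0.34 = 8.2 with RTE. Over 4–7% the range is about 5 (19.4·0.28) to 14 (33.9·0.40). For 45% of 9.7 v 40.6% of 8.2, the standard error of the difference is √(0.2475/9.7 + 0.2412/8.2) = 0.234, so a 95% interval is roughly ±46 points.

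**5. What the trial would observe.** Steps 3 and 4 score against true cancer status. Under Protocol 8.1 a cancer read Thy2 twice is classed as benign. If every miss is read Thy2, only cancers flagged at the first or second FNAC count as malignant:

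- US: 0.60 + 0.18 = 0.78
- RTE at 0.9/0.3: 0.66 + 0.138 = 0.798

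Observed repeat sensitivity is then 100% in both arms. Observed first-FNAC sensitivity is 0.60/0.78 = 76.9% v 0.66/0.798 = 82.7%. Misses read Thy1 or Thy3a can still reach histology and behave differently.

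**The case against.** A reader might infer that the comparison is biased against the arm with the better first FNAC. The documents do not support that. It follows only if RTE helps mainly with cancers that are already easy to detect. Protocol 5.1 also expects RTE to help in large heterogeneous nodules, which is closer to the 0.8/0.5 row, where selection favours RTE. A reader might also take the 15-point deficit in the first row as a forecast. It rests on an extreme detection rate of 1.0, and step 5 shows that the trial's reference standard could hide it entirely.

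The outcome can also be read differently. Repeated FNAC results might mean the whole sequence over all randomised patients, which the all-patients principle in Protocol 8.4 would support. The selection problem then goes away. But item 6 does not say so, and 8.4.2 describes a comparison starting from patients with a benign first result. The whole-sequence reading also has a weakness of its own: a sequence ending in two Thy2 results is judged against a reference that those two results define.

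Defining the population for a secondary outcome could be left to the SAP. That stands in part. However, the between-arm comparison is fixed in the protocol.

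Finally, the question of whether to repeat a Thy2 (Protocol 1.2 and 1.6) compares first and later results within patients. A between-arm repeat contrast does not drive it. That is fair and limits the consequence.

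**Conclusion.** The point holds in a limited form. Protocol 8.1.2 item 6 and 8.4.2 set up a between-arm comparison in a group selected after randomisation by the result under test, and nothing in the protocol corrects for it. That follows from the pathway alone and needs no assumed rates. The direction and size of any bias do depend on assumptions: in the illustrations the repeat-only difference runs from 27 points below the true one (−15 against +12) to about 8 above it (+16.3 against +8). With about 7 to 10 cancers per arm, the contrast could not settle anything even without selection.

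Surgery is not the only exit. Discharge after Thy2 with U2, and MDT discussion after Thy3a, also shape the group. Protocol 1.2 ties surgery for Thy3f, Thy4 and Thy5 to repeated results, whereas 7.1 does not. The two sections must be reconciled because they change who has a repeat.

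This is a minor point on a secondary outcome.

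**What to change.** In Protocol 8.1.2 item 6 and 8.4.2, and in the SAP to match:

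1. Limit between-arm inference on cytology accuracy to the first FNAC in all randomised patients.
2. Report repeat-FNAC accuracy descriptively within each arm, by first result, with counts of patients and of cancers. Include those who left before a repeat and the reason.
3. If a whole-sequence comparison is wanted, define it over all randomised patients, for example as the proportion with histologically confirmed malignancy preceded by Thy3 to Thy5 cytology. State that two Thy2 results define benign under 8.1, so that whole-sequence sensitivity is partly fixed by construction.
4. State that first-FNAC sensitivity depends on the same reference. In the 0.8/0.5 case with all misses read Thy2, a true 60% v 68% would be observed as 0.60/0.78 = 76.9% v 0.68/0.876 = 77.6%.

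This costs wording only and needs no new data. The loss is that repeat-only accuracy is no longer tested between arms.

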8.2. Sample size

We plan to recruit a sample of 968 patients to achieve over 90% power for detecting the following difference in the primary outcome at the 5% significance level, allowing for 15% loss to follow-up.

An audit of US- only guided FNACs in one institution, suggested that Thy1s made up 20% of FNAC results ⁽⁶⁾. This is likely to be an overestimate as this was including cystic nodules, so a more conservative estimate of 10% is assumed in calculating the sample size. The hypothesis is that using RTE in addition to US in guiding the FNAC would reduce the number of Thy1s to 4%. To detect this difference, with a continuity correction, requires 411 patients in each arm or 822 in total. Therefore, after adjusting for 15% drop-out rate, a total of 968 patients is required.

8.3. Projected accrual and attrition rates

Due to variations in their set-up time, centres will on average recruit for a period of 30 months. Each centre will on average recruit 2.5 patients per month during that period, or a total of approximately 30 per year. This is on average 25-30% of the total throughput of the participating centres.

8.4. Statistical Analysis

A separate Statistical Analysis Plan for the ElaTION trial provides a more detailed description of the planned statistical analyses. A brief outline of the planned analyses for the primary and secondary outcome measures which are part of the main trial is given below.

The primary comparison groups will be composed of those who are in the RTE-FNAC arm to those in the US-FNAC arm. Patients, not biopsies, will be the unit of analysis. All analyses will be based on the intention to test and treat principle, with all patients analysed in the arms to which they were allocated irrespective of compliance with the randomised allocated diagnosis tool, and all patients will be included in the analyses. For all tests, summary statistics will be presented and 95% confidence intervals will be constructed where appropriate. A p-value of <0.05 will be considered statistically significant, and there will be no adjustment for multiple comparisons.

8.4.1 Primary Outcome Analysis

The primary outcome analysis will be the proportion of patients in the RTE-FNAC arm who have a Thy1 result following their first FNAC compared with that in the US-FNAC arm.

The primary analysis will be using generalised linear mixed model where the minimisation variables will be included as fixed variables apart from radiologist which will be a included as a random effect. As a secondary analysis, a chi-squared or Fisher's exact test (as appropriate) will be used to compare the proportions of patients who have a Thy 1 first FNAC result between the arms. The denominator will be the number of patients randomised to each arm.

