1.6. The need for ElaTION: a large, multi-centre, randomised controlled trial

In view of conflicting results from some of the retrospective and prospective case series and the fact that most results are single institution reports, a RCT is required to provide evidence of the role of RTE in the diagnosis of thyroid nodules. If proven effective in reducing the need for FNAC and also the false positive rates of FNAC it has the potential to reduce healthcare costs and patient distress significantly. In addition, ElaTION will attempt to answer some of the important outstanding questions in thyroid ultrasonography — mainly the efficacy of ultrasound-only protocols and the need for repetition of Thy2 US FNAC in the diagnosis of thyroid nodules.

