8.5. Missing Data and Sensitivity Analyses

Appropriate sensitivity analysis will be employed to explore the potential bias and reduced statistical power associated with missing data.

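### Dividing Thy1 counts by everyone randomised implicitly scores a missing first-FNAC result as not Thy1, at least in the chi-squared/Fisher test, and does not match the 822 analysable patients of the sample size

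*Protocol*

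**What the plan says.** Protocol section 8.4.1 describes the primary comparison as "the proportion of patients in the RTE-FNAC arm who have a Thy1 result following their first FNAC" against the same proportion in the US-FNAC arm. The primary analysis is a generalised linear mixed model with radiologist as a random effect; a chi-squared or Fisher's exact test is secondary. Directly after that secondary test comes the sentence "The denominator will be the number of patients randomised to each arm".

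Section 8.4 sets out analysis by allocated arm irrespective of compliance, "and all patients will be included in the analyses".

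Section 8.2 sets the target of 968 "allowing for 15% loss to follow-up". It derives 411 analysable patients per arm, 822 in total, and inflates from there.

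On missing data, section 8.5 says only: "Appropriate sensitivity analysis will be employed to explore the potential bias and reduced statistical power associated with missing data". Nowhere does the protocol say how a randomised patient without a first-FNAC result is classified.

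**The concern.** The numerator needs an observed Thy1 result; the denominator does not. A patient who withdraws after randomisation, is not sampled, or whose specimen is lost therefore adds to the denominator only. The protocol does not state this scoring as a rule, but it follows from the wording. Failing to obtain a result then lowers an arm's Thy1 rate, and the comparison mixes two things: how often a sample is inadequate, and how often there is no result.

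Two inconsistencies follow. First, section 8.2 sets aside 15% of patients as lost, whereas section 8.4.1 keeps them in the denominator. Second, a mixed model needs an outcome value for each patient. Without a coding rule it drops patients with no result, while the chi-squared/Fisher test keeps them as not Thy1. The primary and secondary analyses of one endpoint could then use different patients.

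**Working it through.** **Inputs from the protocol.** Thy1 10% (US) and 4% (RTE), 5% significance level, over 90% power, continuity correction, 15% loss (section 8.2); 1:1 allocation (section 4.1). Two-sided testing is assumed because it reproduces the stated figure. **Assumed:** the share missing in each arm, since the protocol gives no rate by arm, and missingness unrelated to Thy1 status within an arm.

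**1. Reproduce the sample size.** The mean rate is 0.07.

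n = [1.96·√(2·0.07·0.93) + 1.2816·√(0.10·0.90 + 0.04·0.96)]² / 0.06² = 377.9 per arm.

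With continuity correction: n/4·[1 + √(1 + 4/(n·0.06))]² = 410.6, so 411 per arm and 822 in total. Then 822/0.85 = 967.1, giving 968, or 484 per arm. The plan's figures reproduce, and they rest on 822 analysable patients.

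**2. Effect of the denominator.** Observed rate = true rate × (1 − share missing).

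**3. Equal loss, 15% in both arms.** 0.10 × 0.85 = 8.5% and 0.04 × 0.85 = 3.4%. The risk ratio stays at 0.40; the difference falls from 6.0 to 5.1 points. Continuity-corrected power is 89.7% with 484 per arm in the denominator, against 90.0% on 411 analysable patients per arm, so equal loss costs almost no power.

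**4. Unequal loss, no true effect.** Two-sided pooled z-test, 484 per arm. Example with 5% missing in US and 15% in RTE:

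- Observed 9.5% v 8.5%, d = 0.010, mean 0.09.
- Null SE = √(2·0.09·0.91/484) = 0.018396; critical difference = 1.96 × 0.018396 = 0.03606.
- SE under the observed rates = 0.018394.
- Rejection = Φ[(0.010 − 0.03606)/0.018394] + Φ[(−0.010 − 0.03606)/0.018394] = 0.0783 + 0.0061 = 8.4%.

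| Thy1 rate, both arms | Missing US / RTE | Observed US v RTE | False positives, uncorrected | With continuity correction |
|---|---|---|---|---|
| 10% | 0 / 0 | 10.0% v 10.0% | 5.0% | 3.9% |
| 10% | 0 / 5% | 10.0% v 9.5% | 5.8% | 4.5% |
| 10% | 5% / 15% | 9.5% v 8.5% | 8.4% | 6.8% |
| 10% | 0 / 15% | 10.0% v 8.5% | 12.7% | 10.5% |

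The correction subtracts 1/484 from the absolute difference.

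**5. Unequal loss, planned effect of 10% v 4%.** With 15% missing in US and 5% in RTE: 0.10 × 0.85 = 8.5% and 0.04 × 0.95 = 3.8%, a difference of 4.7 points. Uncorrected power is 86.2%, against 95.6% with nobody missing.

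**6. The scoring rule can decide the direction.** Take true rates of 10% v 4% with 15% missing in the RTE arm only. Missing as not Thy1 gives 10.0% v 3.4%. Missing as Thy1 gives 10.0% v 0.04 × 0.85 + 0.15 = 18.4%.

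**The case against.** **The sentence may govern only the secondary test.** It directly follows the chi-squared/Fisher sentence, and a mixed model fitted to observed results would already use evaluable patients. This stands as a possible reading, so a flat statement that the primary analysis scores missing results as not Thy1 goes further than the text. On this narrow reading the two analyses use different patient sets; on the wide reading, supported by "all patients will be included in the analyses" in section 8.4, the primary model is affected too. Either way the text needs settling.

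**Intention to treat requires it.** Analysis by allocated arm does not require counting an unknown result as favourable.

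**Detail belongs in the SAP.** The SAP is not shown and may define missing-result handling. That answers the thinness of section 8.5, but not a denominator that the protocol itself fixes.

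**A mechanism for unequal loss.** A reader might infer from "If proven effective in reducing the need for FNAC" in section 1.6 that the protocol expects fewer first FNACs in the RTE arm. It does not support that. The phrase describes benefit if RTE is proven effective. Sections 5.1 and 5.2 include FNAC in both arms, and section 3.2 identifies patients before a session for US-FNAC. Unequal loss is possible but not foreseen.

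**The size is modest.** This largely stands. At a 10% rate, about 35% missing in the RTE arm alone is needed before expected counts by themselves reach p<0.05 under no effect. False-positive rates are higher at a 20% Thy1 rate (12.8% and 22.5% for the last two rows of the table), but section 8.2 considers 20% likely too high here because that audit included cystic nodules.

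**The evaluable set is not automatically unbiased.** Correct: it conditions on an event after randomisation. It therefore needs support from analyses of all randomised patients.

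**Conclusion.** The point holds as an inconsistency in how the primary endpoint is defined. Sections 8.2, 8.4 and 8.4.1 cannot all describe one analysis, and the literal wording gives favourable credit for a missing result, certainly in the chi-squared/Fisher test and possibly in the mixed model. Equal loss leaves the risk ratio intact and only shrinks the difference. Unequal loss distorts the comparison in either direction: within the protocol's own 15%, from almost nothing (5% v 0%) to roughly two and a half times the nominal false-positive rate (15% v 0%), or a loss of about nine points of power.

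These sizes rest on assumed shares by arm, no covariate or radiologist adjustment, and missingness unrelated to Thy1 status. They show what the rule permits; they do not predict what will happen in this trial.

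**What to change.** Replace the denominator sentence in section 8.4.1 with wording such as: *The denominator will be randomised patients with a first-FNAC cytology result, analysed in the arm allocated.* Say that this set applies to both the mixed model and the chi-squared/Fisher test, and align the all-patients statement in section 8.4 with it. Tabulate patients with no FNAC or no result by arm and reason.

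Because the evaluable set can be biased if sampling depends on arm, name three sensitivity analyses on all randomised patients:

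- multiple imputation of the missing result using arm, the minimisation variables and radiologist;
- missing counted as Thy1;
- missing counted as not Thy1, which keeps the result under the present wording visible.

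The cost is a short text change, one table and a little extra analysis. The sample size does not change, because the 822 patients in section 8.2 already correspond to the evaluable set.
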